7.2. Recording Adverse Events and Serious Adverse Events

Recording of adverse events and serious adverse events:

- The investigator or site staff will be responsible for detecting, documenting and reporting events that meet the definition of an AE or SAE.
- The investigator or site staff will then record all relevant information regarding an AE/SAE in the CRF.
- There may be instances when copies of medical records for certain cases are requested by GSK. In this instance, all subject identifiers, with the exception of the subject number, will be blinded on the copies of the medical records prior to submission to GSK.
- The investigator will attempt to establish a diagnosis of the event based on signs, symptoms, and/or other clinical information. In such cases, the diagnosis will be documented as the AE/SAE and not the individual signs/symptoms. Clinical AEs will be described by diagnosis and not by symptoms when possible (e.g., upper respiratory tract infection, seasonal allergy, etc. instead of runny nose).
- AEs will be collected from the start of the washout product and until 5 days following last administration of the study product.
- SAEs will be collected over the same time period as stated above for AEs. However, any SAEs assessed as **related** to study participation (e.g., investigational product, protocol mandated procedures, invasive tests, or change in existing therapy) or related to a GSK concomitant medication will be recorded from the time a subject consents to participate in the study up to and including any follow-up contact.
- Medical conditions reported prior to the time period for reporting AEs/SAEs should be recorded as part of the subject's medical history.

7.3. Evaluating Adverse Events and Serious Adverse Events

Assessment of Intensity:

The investigator or designee will make an assessment of intensity for each AE and SAE reported during the study and will assign it to one of the following categories:

- Mild: An event that is easily tolerated by the subject, causing minimal discomfort and not interfering with everyday activities.
- Moderate: An event that is sufficiently discomforting to interfere with normal everyday activities
- Severe: An event that prevents normal everyday activities. - an AE that is assessed as severe will not be confused with an SAE. Severity is a category utilized for rating the intensity of an event; and both AEs and SAEs can be

Document Name	Clinical Protocol 207468.doc		
Type	Version	Document Identifier	Effective Date
elido_controlled	3.0; Most-Recent; Effective; CURRENT	090032d580d15804	24-Mar-2017 07:31:33
Reason For Issue	Auto Issue		

assessed as severe.
 Note: An event is defined as 'serious' when it meets at least one of the pre-defined outcomes as described in the definition of an SAE.

Assessment of Causality:

- The investigator is obligated to assess the relationship between study product and the occurrence of each AE/SAE.
- A "reasonable possibility" is meant to convey that there are facts/evidence or arguments to suggest a causal relationship, rather than a relationship cannot be ruled out.
- The investigator will use clinical judgment to determine the relationship.
- Alternative causes, such as natural history of the underlying diseases, concomitant therapy, other risk factors, and the temporal relationship of the event to the study product will be considered and investigated.
- The investigator will also consult the Investigator Brochure (IB) and/or Product Information, for marketed products, in the determination of his/her assessment.
- For each AE/SAE the investigator **must** document in the medical notes (source document) or CRF that he/she has reviewed the AE/SAE and has provided an assessment of causality.
- There may be situations when an SAE has occurred and the investigator has minimal information to include in the initial report to GSK. **However, it is very important that the investigator always make an assessment of causality for every event prior to the initial transmission of the SAE data to GSK.**
- The investigator may change his/her opinion of causality in light of follow-up information, amending the SAE data collection tool accordingly.
- The causality assessment is one of the criteria used when determining regulatory reporting requirements.

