2. OBJECTIVES AND ENDPOINTS

Objectives	Endpoints
Primary	
Evaluation of wrinkle dimensions (change from baseline) of test product compared to no treatment on the Periocular / Crow's Feet Area.	DermaTOP parameter R_a at 4 weeks.
Secondary	
Evaluation of wrinkle dimensions (change from baseline) of test product and positive control compared to no treatment in the Periocular / Crow's Feet Area.	DermaTOP parameter R_a at 2 weeks and 4 weeks (positive control only)
	DermaTOP parameters R_z , S_a and S_{tm} at 2 and 4 weeks
	Clinical Fitzpatrick Wrinkle Score at 2 and 4 weeks
Evaluation of skin moisturisation (change from baseline) of test product and positive control compared to no treatment	Instrumental Corneometer values at 2 and 4 weeks

Document Name	Clinical Protocol 207468.doc		
Type	Version	Document Identifier	Effective Date
eldo_controlled	3.0; Most-Recent; Effective; CURRENT	090032d580d15804	24-Mar-2017 07:31:33
Reason For Issue	Auto Issue		

on the Sub-ocular/ Cheek Area.	
Evaluation of texture (change from baseline) of test product and positive control compared to no treatment on the full face.	Texture ranking at 4 weeks
Evaluation of skin elasticity (change from baseline) of test product and positive control compared to no treatment on the Sub-ocular/ Cheek Area.	Instrumental Cutometer parameters R5 and R7 at 2 and 4 weeks
Evaluation of skin barrier (change from baseline) of test product and positive control compared to no treatment on the Sub-ocular/ Cheek Area.	Instrumental Trans-Epidermal Water Loss (TEWL) values at 2 and 4 weeks
To evaluate the general safety of the study products	Assessment of frequency and severity of Adverse Events (AEs)

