9.3.6.2	Analysis of Texture Rankings Based on USR-CliP Images – Change from baseline – ITT Population		Appendix 3
9.4.1	Treatment-Emergent Adverse Events – Safety Population	X	

Document Name	Statistical Analysis CCI	207468.docx	
Type	Version	Document Identifier	Effective Date
eldo_clinical_doc	1.0; CURRENT; Most-Recent; Effective	090032d580d23463	10-Apr-2017 13:34:23
Reason For Issue	Auto Issue		

9.4.2	Treatment-Emergent Treatment-Related Adverse events – Safety Population	X	
9.4.3	Treatment-Emergent Adverse Events by Severity – Safety Population	X	
9.4.4	Treatment-Emergent Treatment-Related Adverse Events by Severity – Safety Population	X	

All listings to be generated are the standard set.

 GlaxoSmithKline	Document Name	Statistical Analysis CCI 207468.docx		
	Type	Version	Document Identifier	Effective Date
	eldo_clinical_doc	1.0; CURRENT; Most-Recent; Effective	090032d580d23463	10-Apr-2017 13:34:23
	Reason For Issue	Auto Issue		

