### Section: 9 Safety Analysis

**Reason for amendment:** Reference to additional pre-unblind step of assigning application site(s) AE's to treatment at that site(s).

**Original text:** Treatment emergent AEs are defined as events that start on or after the first treatment date. Events occurring following the start of treatment which were also reported before treatment began with no change in severity or causality will however not be considered treatment emergent.

AEs will be tabulated according to the current version of the MedDRA. Frequencies and percentages will be presented by product group and overall, for each system organ class, and for each preferred term. Summaries of treatment-emergent AEs, treatment-related treatment-emergent AEs, AEs leading to discontinuation, and serious AEs will be completed.

**Amendment:** Treatment emergent AEs are defined as events that start on or after the first treatment date. Events occurring following the start of treatment which were also

Document Name	SAP Amendment 207648.doc		
Type	Version	Document Identifier	Effective Date
eldo_clinical_doc	1.0; CURRENT; Most-Recent; Effective	090032d580d54792	12-Jun-2017 07:04:24
Reason For Issue	Auto Issue		

reported before treatment began with no change in severity or causality will however not be considered treatment emergent.

AEs will be tabulated according to the current version of the MedDRA. Frequencies and percentages will be presented by product group and overall, for each system organ class, and for each preferred term. Summaries of treatment-emergent AEs, treatment-related treatment-emergent AEs, AEs leading to discontinuation, and serious AEs will be completed.

**A further step will take place pre-unblind to flag the AEs by application site if appropriate so that attribution to applied treatment is preserved. This will involve review of all application site AEs and addition of a flag to indicate which site(s) it is applicable to.**

Document Name	SAP Amendment 207648.doc		
Type	Version	Document Identifier	Effective Date
eldo_clinical_doc	1.0; CURRENT; Most-Recent; Effective	090032d580d54792	12-Jun-2017 07:04:24
Reason For Issue	Auto Issue		

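### A facial adverse event gets one intensity and one causality rating, and its side is flagged only afterwards, so a two-sided reaction entered once shows the same rating in both arms

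*Protocol*

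**What the plan says.** Protocol section 2 and SAP section 2 make the frequency and severity of adverse events the safety endpoint.

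- **Recording (Protocol 7.2).** Where a diagnosis can be made, "the diagnosis will be documented as the AE/SAE and not the individual signs/symptoms".
- **Rating (Protocol 7.3).** "The investigator or designee will make an assessment of intensity for each AE and SAE reported during the study", and that person "will assign it to one of the following categories": mild, moderate or severe. The categories describe the whole subject. Mild, for example, is "An event that is easily tolerated by the subject, causing minimal discomfort and not interfering with everyday activities". Causality is likewise assessed once per event.
- **Asking (Protocol 7.4 and Schedule of Events).** The standard question to subjects does not mention side of face, and the schedule has no tolerability score by side.
- **Attribution (SAP amendment, section 9).** "A further step will take place pre-unblind to flag the AEs by application site" where appropriate. The amendment continues: "This will involve review of all application site AEs and addition of a flag to indicate which site(s) it is applicable to".
- **Reporting.** Protocol 9.3.4 tabulates events by treatment arm, and SAP section 9 by product group and overall. SAP Appendix 2 sets three treatment labels for all outputs. Table 9.4.3 is "Treatment-Emergent Adverse Events by Severity", Table 9.4.4 is its counterpart for treatment-related events, and Table 9.4.2 shows treatment-related events.

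**The concern.** Efficacy is measured separately on each half-face. Adverse events are collected per subject and assigned to half-faces later. The amendment restores the location of an event. It cannot by itself supply an intensity, causality rating or onset date for each side if these were not captured when the event was reported.

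Suppose a dermatitis is worse on one side than on the other. Entered once, it has one grade and one causality rating. Flagged to both sites, it appears with those same ratings under both products, or under a product and No Treatment. The severity and relatedness tables then show no difference on a face where there was one. Every subject has self-reported sensitive skin, so reactions on both sides are plausible.

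**Working it through.** **What the documents give.** They state no adverse event rates, so there is no safety figure to reproduce. The only power figure (40 subjects, 0.46 SD, about 80%) concerns R_a and is not an input here. It does reproduce: 81.0% from the noncentral t distribution.

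**Step 1: one face.** Let the true grades be gA and gB, and let g be the single recorded grade. The true within-face contrast is gA − gB. With one record flagged to both sites, the tabulated contrast is g − g = 0 whatever rule produced g. If gA = gB, nothing is lost. If only one side reacts, only that side is flagged and nothing is lost. The same reasoning applies to causality. Table 9.4.1, which uses neither rating, still counts the event correctly on both sides.

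**Step 2: the pooled three-arm table.** With 72 randomised and equal allocation there are 72/3 = 24 subjects per pair and 2 × 24 = 48 half-faces per arm. Assume that a share b of subjects with a positive-control side have a two-sided reaction, moderate on that side and mild on the other, and that the single grade follows the worse side. For b = 10%, moderate-or-worse events are:

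- positive control: 2 × 24 × 0.10 / 48 = 10%, under either method;
- test product: 0% if graded by side, 24 × 0.10 / 48 = 5% if graded once;
- positive control minus test product: 10 points if graded by side, 5 if graded once.

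For b = 5% and 20% this difference goes from 5 to 2.5 and from 20 to 10 points. If only half of the two-sided reactions are unequal, the figures for b = 5/10/20% are 2.5/5/10 points by side and 1.25/2.5/5 graded once. If none are unequal, both are 0.

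Another contrast can move the other way. If untreated sides do not react, No Treatment stays at 0%, and test product minus No Treatment rises from a true 0 to 2.5/5/10 points for b = 5/10/20%.

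**Step 3: one pair with random severity.** For test product/no treatment, assume latent severity = subject effect (SD 1) + side effect (SD 0.5 to 0.7) + product effect (0.5 to 1.0), cut at 1.2, 2.0 and 2.8 into none, mild, moderate and severe. The worse grade is given to every affected side. Moderate-or-worse rates, product side versus untreated side:

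| True | As tabulated | Difference (points) | Share lost |
|---|---|---|---|
| 8.9% vs 3.6% | 9.7% vs 7.2% | 5.3 to 2.5 | 2.8/5.3 = 53% |
| 14.4% vs 5.1% | 15.6% vs 9.4% | 9.3 to 6.2 | 3.1/9.3 = 33% |
| 18.6% vs 3.7% | 19.0% vs 10.4% | 14.9 to 8.6 | 6.3/14.9 = 42% |

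Over this range of assumptions the loss runs from 31% to 53%. The cut-points imply some adverse event on about 26% to 44% of product sides and 14% to 16% of untreated sides, which is high for a moisturiser. In a pair of 24 subjects the shift is small in absolute terms: 24 × 0.028 = 0.7 to 24 × 0.063 = 1.5 half-faces.

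**The case against.** The strongest reply is that one entry per two-sided reaction is an inference. The diagnosis rule in 7.2 concerns diagnosis versus symptoms, not laterality. The same section tells staff to record all relevant information, the CRF is not in the documents, and no text forbids one entry per side. The flag review itself needs some location information. This stands, and it makes the point conditional. It does not remove it: nothing asks for entries by side, and the amendment's wording allows one event to carry more than one site.

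Second, only unequal two-sided events are affected. A reaction to the shared cleanser would tend to be symmetric, and a reaction to one product would tend to be one-sided. That also stands and limits the likely frequency.

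Third, the intensity scale measures interference with the subject's everyday activities, so a grade per half-face has no meaning on it as written. This is correct, and the fix has to deal with it.

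Fourth, the safety output is descriptive, with no test planned, in a small proof-of-concept study. That supports a modest rating.

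A reader might infer more than the documents support:

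- *Severity comparisons are biased towards no difference.* This is true only between the two treatments on one face. Step 2 shows a pooled contrast rising.
- *The event is graded at its worse side, or by a sponsor review.* Protocol 7.3 sets no worst-side rule, and the amendment names no reviewer.
- *The split-face design loses its within-subject control for safety.* One-sided events and frequency by side are preserved by the flag.

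**Conclusion.** The point holds as a cheap improvement. Each adverse event has one intensity and one causality rating, side is not requested at reporting, and the later flag adds location only. If a two-sided facial reaction is entered as one event, its ratings go into both arms, and any within-face difference is lost from the by-severity tables (9.4.3 and 9.4.4) and the treatment-related tables (9.4.2 and 9.4.4). For such an event the tabulated within-face contrast is exactly zero under any grading rule.

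The overall size cannot be derived from the documents. About one third to one half of the within-pair difference in moderate-or-worse events is an illustration that rests on worst-side grading, assumed severity distributions and high event rates. Contrasts between different faces can move in either direction.

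**What to change.** **Protocol 7.2 and 7.3, and the adverse event CRF page.** For any event on the face, record right, left or both when it is reported. If both, record intensity, causality, onset date and end date for each side. State that intensity is then judged for the reaction on that side, because the existing categories refer to the whole subject.

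**SAP section 9.** Build the by-product tables (9.4.1 to 9.4.4) for facial events from these side-level data, say how two-sided events are counted, and count each subject once in the overall column. Keep the pre-unblinding flag review only as a check.

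**Cost.** A few extra CRF fields, one completion instruction and a short SAP addition. A two-sided event produces two entries, so overall figures must be counted by subject. Recording right or left does not itself reveal which product was applied there.

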7.4. Reporting Adverse Events and Serious Adverse Events

AE Reporting to GSKCH:

- AEs will be recorded in the AE section of the CRF.
- Medical conditions recorded by the subject on a diary card or similar document that meet the definition of an AE must also be recorded in the AE section of the CRF, if not previously well-characterized by the investigator in the subject's medical history.
- AEs elicited by the investigator in a standard manner at the study visits should also be recorded in the AE section of the CRF. The investigator or designee must ask the subject the following question during each visit including any follow-up visits: **"Have you felt unwell, experienced any symptoms or taken any medication (since your last visit) (today) (since your last dose) (since the**

Document Name	Clinical Protocol 207468.doc		
Type	Version	Document Identifier	Effective Date
eldo_controlled	3.0; Most-Recent; Effective; CURRENT	090032d580d15804	24-Mar-2017 07:31:33
Reason For Issue	Auto Issue		

last session)?”

- The medically qualified investigator should review adverse events in a timely manner; this review should be documented in writing in the source document or in the CRF.
- After the study is completed at a given site, and the site has received their study data on Compact Discs (CDs), the electronic data collection tool will be removed from the internet to prevent the entry of new data or changes to existing data.

SAE Reporting to GSKCH:

A paper copy of the SAE form provided in the investigator study master file should be completed as fully as possible.

It is essential to enter the following information:

- Protocol and subject identifiers
- Subject's demography
- Description of events, with diagnosis if available
- Investigator opinion of relationship to study product (see section 7.3)
- Criterion for seriousness.

The following are desirable and are of particular relevance for investigator and GSKCH assessment of the SAE report:

- Date of onset of AE
- Date AE stopped, if relevant
- Study product start date
- Study product end date if relevant
- Action taken on study product
- Outcome if known

The SAE form, completed as fully as possible, and SAE fax cover sheet must be faxed or e-mailed to the appropriate GSKCH Study Manager as soon as possible, **but not later than 24 hours** after study site personnel learn of the event. The GSKCH Study Manager should be notified of the situation by telephone or email.

Fax Serious Adverse Events to:

UK: PPD

The GSKCH Study Manager will be responsible for forwarding the SAE form to the Case Management Group, Global Clinical Safety and Pharmacovigilance, the Medical Director responsible for the study and other GSKCH personnel as appropriate via email.

The initial report will be followed up with more information as relevant, or as requested by the GSKCH study manager.

Document Name	Clinical Protocol 207468.doc		
Type	Version	Document Identifier	Effective Date
eldo_controlled	3.0; Most-Recent; Effective; CURRENT	090032d580d15804	24-Mar-2017 07:31:33
Reason For Issue	Auto Issue		

7.5. Follow-up of Adverse Events and Serious Adverse Events

Follow-up of AEs and SAEs:

- After the initial report, the investigator is required to proactively follow up with each subject and provide further information on the subject's condition.
- All AEs/SAEs will be followed until resolution, until the condition stabilizes, until the event is otherwise explained, or until the subject is lost to follow-up.
- The investigator is obligated to perform or arrange for the conduct of supplemental measurements and/or evaluations as may be indicated or as requested by GSK to elucidate as fully as possible the nature and/or causality of the AE or SAE.
- Investigators are not obliged to actively seek AEs or SAEs in former subjects. However, if the investigator learns of any SAE, including the death, at any time after a subject has been discharged from the study, and considers the event reasonably related to the investigational product or study participation, the investigator will promptly notify GSKCH.
- The investigator will submit any updated SAE data to GSK within the designated reporting time frames.

Regulatory and ethics reporting requirements for SAEs:

- The investigator will promptly report all SAEs to GSKCH within the designated reporting timeframes (within 24 hours of learning of the event). GSKCH has a legal responsibility to notify, as appropriate, the local regulatory authority and other regulatory authorities about the safety of a product under clinical investigation. Prompt notification of SAEs by the investigator to GSKCH is essential so that legal obligations and ethical responsibilities towards the safety of subjects are met.
- GSKCH will comply with country specific regulatory requirements relating to safety reporting to the regulatory authority, IEC and investigators.
- Investigator safety reports are prepared according to GSKCH policy and are forwarded to investigators as necessary. An investigator safety report is prepared for a SAE(s) that is both attributable to investigational product and unexpected. The purpose of the report is to fulfil specific regulatory and GCP requirements, regarding the product under investigation.
- An investigator who receives an investigator safety report describing a SAE(s) or other specific safety information (e.g., summary of listing of SAEs) from GSKCH will file it with the Investigator Brochure (or safety statement) and will notify the IEC, if appropriate according to local requirements.

Document Name	Clinical Protocol 207468.doc		
Type	Version	Document Identifier	Effective Date
eldo_controlled	3.0; Most-Recent; Effective; CURRENT	090032d580d15804	24-Mar-2017 07:31:33
Reason For Issue	Auto Issue		

7.6. Collection of Pregnancy Information

7.6.1. Time Period for Collecting of Pregnancy Information

Collection of Pregnancy Information:

- Pregnancy information will be collected on all pregnancies reported following administration of washout product. Information on pregnancy identified during the screening phase and prior to washout product administration does not need to be collected.

